We would like to research upon the efficacy of ultrasound-guided fistuloplasty as an alternative to fluoroscopy-guided fistuloplasty to prolong patency of patients with arteriovenous access flow dysfunction.

2. Objective

To determine the efficacy of ultrasound-guided fistuloplasty compared to fluoroscopy-guided fistuloplasty in patients with arteriovenous access flow dysfunction.

3. Methodology

Study design: Multicentre, randomized controlled trial.

Location: Hospital Kuala Lumpur and University Malaya Medical Centre.

Population: Vascular clinic patients in Kuala Lumpur Hospital and University Malaya Medical Centre.

1. Treatment group: Patients who underwent ultrasound-guided fistuloplasty for arteriovenous access flow dysfunction are assessed prospectively for a period of 6 months.
2. Control group: Patients who underwent fluoroscopy-guided fistuloplasty for arteriovenous access flow dysfunction are assessed prospectively for a period of 6 months.

Sampling method: Simple random sampling.

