3.1 Study Type and Design

This is an experimental study employing a prospective randomized controlled trial.

The primary outcome would be to compare the patency of arteriovenous fistula at one, three and six months.

Secondary outcomes shall include:

- To capture data regarding variables that may affect patency of arteriovenous access flow dysfunction post ultrasound-guided fistuloplasty versus fluoroscopy-guided fistuloplasty,
- To compare technical success (defined as clinical palpable thrill, radiographic finding of less than 30% recoil and ultrasonographic finding of continuous segment of dilated vein to 5-6mm and continuous flow rate of more than 500ml/min) in patients with arteriovenous access flow dysfunction receiving ultrasound-guided fistuloplasty versus fluoroscopy-guided fistuloplasty and
- To compare complication rates in patients with arteriovenous access flow dysfunction receiving ultrasound-guided fistuloplasty versus fluoroscopy-guided fistuloplasty

Patients are randomized using simple randomization method. Treatment plans are divided equally between ultrasound-guided fistuloplasty and fluoroscopy-guided fistuloplasty. An application “sealedenvelope.com” is used for this purpose. The application does this via a built in random number generator.

After assessing for eligibility, patients will be randomized equally with a ratio 1:1 to ultrasound-guided fistuloplasty group and fluoroscopy-guided fistuloplasty group.

Both interventions will be done in operation theatre to maintain sterility. After cleaning and draping the area of interest, local anaesthesia is given to the puncture site. A puncture needle is used to gain access to the arteriovenous fistula followed by a guide wire. Then, a sheath with an appropriate size is placed and a balloon catheter of adequate size is inserted over the guide wire and inflated for 2 minutes. Ultrasound is used in the subject group to monitor technical success. On table visualization of continuous segment of dilated vein to 5-6mm and continuous flow rate of more than 500ml/min signifies the end points of the procedure.

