Fluoroscopy is used in the control group to assess for technical success. On table fistulogram visualization of less than 30% recoil of the target lesion signifies technical success. After a satisfactory result, a figure of 8 suture is placed with manual inflow occlusion. Post procedure, patients will be observed for any signs of haematoma or bleeding. If there are no immediate complications, patients will be discharged on the same day.

These procedures will be performed either by vascular surgeons or interventional radiologists below tabled:

OPERATOR	FISTULOPLASTY		CENTRE	DESIGNATION
	ULTRASOUND-GUIDED	FLUOROSCOPY-GUIDED		
[name] [name]	✓		University Malaya Medical Centre	Vascular surgeon
TBD		✓	University Malaya Medical Centre	Interventional radiologist
[name] [name]	✓	✓	Hospital Kuala Lumpur	Vascular surgeon

Cases with serious complications such as extravascular leak or significant pseudoaneurysm will be admitted for monitoring. If the complications are resolved then, the patient will be discharged. Follow-up may be scheduled earlier.

Follow-up will be done at two weeks, one month, three months and six months.

Assessment during follow-up includes:

- Resolution of symptoms (prolonged post dialysis bleeding or difficult access cannulation).
- Reduction of venous dialysis pressure to below predefined threshold values. (the acceptable value is less than 150mmHg)
- Measurement of the volume flow (the acceptable value is more than 500ml/min), flow characteristics (the acceptable characteristic is laminar flow) and diameter of the target lesion (the acceptable diameter is between 5-6mm) using duplex ultrasound.

[figure not shown]
In the event of a negative outcome during the first post fistuloplasty follow-up, it will be determined whether it is due to:

- a missed stenotic segment invisible to ultrasound or
- it is a case of severe stenotic segment refractory to fistuloplasty.

Patients belonging to the former category will cross-over to the fluoroscopic-guided fistuloplasty group. In the latter case, there is no reason to repeat the fistuloplasty regardless of the imaging method (ultrasound or fluoroscopy). Ideally, these particular patients should receive drug-coated balloon (DCB) fistuloplasty which is beyond the scope of this study. There is no alternative apart from switching to fluoroscopic-guided fistuloplasty.

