3.6 Sample Size

Based on a power of 80% ($\beta=0.2$), alpha of 0.05, a response anticipated difference of 90% in ultrasound-guided fistuloplasty group and 52.4% in fluoroscopy-guided fistuloplasty group, the calculated sample size for each group is 22 patients. Allowing for 20% dropout, a final sample size of 27 per group will be used.

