3.9 Statistical Analysis Plan

The data analysis will be done using the SPSS version 26.0 Descriptive date will be expressed as mean \pm standard deviation (SD) for numerical data and frequency (percentage) for categorical data. Independent t-test will be used to analyse the primary objective. Secondary objective will be analyzed using logistic regression. A value of $P < 0.05$ is considered statistically significant. The data collected will be analyzed using an per protocol basis.

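### One-way crossover after an early poor result, combined with an undefined per-protocol-only analysis, can tilt six-month patency towards ultrasound

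*Combined protocol and SAP*

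**What the plan says.** Section 3.1 sets the endpoint: "The primary outcome would be to compare the patency of arteriovenous fistula at one, three and six months". It does not say whether this is primary patency or whether a repeat procedure ends it.

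The same section sorts a negative first follow-up (the first visit is at two weeks) into two causes. The first is "a missed stenotic segment invisible to ultrasound", and for it the instruction is: "Patients belonging to the former category will cross-over to the fluoroscopic-guided fistuloplasty group". The second is a refractory stenosis. The text sees no point in repeating the procedure for these patients under either imaging method, yet ends: "There is no alternative apart from switching to fluoroscopic-guided fistuloplasty". What makes a follow-up negative is not defined.

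Section 3 (Methodology) describes the treatment group as "Patients who underwent ultrasound-guided fistuloplasty for arteriovenous access flow dysfunction are assessed prospectively for a period of 6 months" and the control group as "Patients who underwent fluoroscopy-guided fistuloplasty for arteriovenous access flow dysfunction are assessed prospectively for a period of 6 months". Neither description refers to randomised allocation.

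Section 3.9 states the analysis population in one sentence: "The data collected will be analyzed using an per protocol basis". It does not define the per-protocol set, does not say how crossovers count, and gives no analysis by randomised arm.

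**The concern.** The only destination named is fluoroscopy, so a fluoroscopy-arm patient has nowhere to cross to. The patients who change group are therefore ultrasound patients, selected by a poor early outcome. A per-protocol set normally leaves out patients who depart from their assigned treatment. Applied here, it would remove early failures from one arm and keep the matching failures in the other.

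The arm descriptions do not settle the matter, because a crossover patient has had both procedures and fits both. Without a rule, such a patient could be dropped, counted under fluoroscopy, kept as an ultrasound failure, or kept under ultrasound and scored patent after fluoroscopic rescue. The choice could be made after outcomes are known. At stake is the comparison the trial exists to make, in a sample where one or two patients can move the result.

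**Working it through.** **Inputs.** Section 3.6 gives 90% versus 52.4%, alpha 0.05 and power 80%, and states that "the calculated sample size for each group is 22 patients". Appendix 1 gives one-month ultrasound patency for six series: 100, 94.4, 93, 96, 100 and 100%. It also gives 77.6% as one of the six-month figures. The documents give no crossover rate, so one crossover is an assumption.

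**The plan's own figure.** Two proportions, two-sided (assumed; sidedness is not stated), pooled variance under the null, mean proportion 0.712:

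n = [1.96 × √(2 × 0.712 × 0.288) + 0.842 × √(0.90 × 0.10 + 0.524 × 0.476)]² / 0.376² = (1.255 + 0.490)² / 0.1414 ≈ 21.6, so 22 per group. The figure reproduces.

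**How many crossovers to expect.** Early failure at one month runs from 0% to 7% in Appendix 1. Of 22 patients that is 22 × 0 = 0 to 22 × 0.07 = 1.5. Three of the six series imply none.

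**Set-up.** Two independent Binomial(22, p) arms with the same true p, enumerated exactly. If the ultrasound arm has at least one six-month failure, one of them is the crossover and is handled as stated. The result is the probability that a pooled two-proportion z exceeds 1.96 in favour of ultrasound. The independent t-test named in section 3.9, applied to 0/1 patency, gives the same values.

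**False gap when the crossover is dropped.** Expected ultrasound patency is (22p − p²²)/21, where the p²² term covers trials with no ultrasound failure to drop. Subtract p:

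- p = 0.524: 11.528/21 − 0.524 = 2.5 points (p²² is negligible).
- p = 0.776: (17.072 − 0.004)/21 − 0.776 = 3.7 points.
- p = 0.90: (19.8 − 0.098)/21 − 0.90 = 3.8 points.

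**Chance of a significant result for ultrasound when the arms are truly equal.**

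| Handling of the one crossover | p = 52.4% | p = 77.6% | p = 90% |
|---|---|---|---|
| Kept as an ultrasound failure | 2.4% | 2.5% | 2.2% |
| Dropped | 4.8% | 6.5% | 6.4% |
| Kept in ultrasound, scored patent | 4.8% | 7.0% | 6.4% |
| Counted under fluoroscopy, patent | 2.7% | 5.3% | 6.0% |
| Counted under fluoroscopy, failed | 5.0% | 9.1% | 11.4% |
| Dropped, and one fluoroscopy failure dropped too | 2.7% | 4.0% | 2.2% |

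**A variable number of crossovers.** Suppose instead that each ultrasound patient has a 4% or 7% chance of early failure and all such patients are dropped. The chance is then 3.7% or 4.7% at p = 52.4%, and 4.5% or 6.8% at p = 77.6%.

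**The case against.** **The effect may be negligible.** Entry requires a Doppler-confirmed stenosis (section 3.3) and suspected central vein or cephalic arch stenosis is excluded (section 3.4), so segments that ultrasound cannot see should be rare. A gap of 2.5 to 3.8 points is small beside the planned 90 − 52.4 = 37.6. If the undefined set also removed an early fluoroscopy failure, the error would be close to nominal at two of the three rates. All of this stands and limits the size. It does not remove the asymmetry, because no text provides for removing fluoroscopy failures. The undefined trigger could also be wider than lost patency, though the documents give no figure for that.

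**A rule may exist in material that cannot be seen.** A figure in section 3.1 and the CONSORT flowchart are not shown. That no fluoroscopy-arm patient can cross over is inferred from the sole destination; no sentence says it. The point therefore rests on the text. The analysis section itself is visible and has no rule.

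**Patency after rescue is a legitimate endpoint.** This is right for a strategy of ultrasound first with fluoroscopic rescue. It is a different endpoint from the primary patency tabulated in Appendix 1, and the plan does not say which it means.

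**Counting a crossover under fluoroscopy is a strained reading.** It sits badly with the exclusion of prior fistuloplasty in section 3.4, although section 3.1 does speak of crossing to that group. The 9.1% and 11.4% figures should not drive the judgement.

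**Counting every crossover as an ultrasound failure could bias the other way.** This also stands. Section 3.1 prescribes re-treatment in one arm only, on an undefined trigger. A borderline ultrasound patient would fail automatically, while a fluoroscopy patient with the same finding could still be read as patent at six months. The remedy needs one trigger for both arms.

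**Conclusion.** The concern holds as a fault of method that should be corrected. Followed as written and read in the ordinary way, the plan can drop early failures from the ultrasound arm only. That biases six-month patency towards ultrasound. Moving them to fluoroscopy pushes the same way, and scoring them patent after rescue changes the endpoint.

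The size is unknown and probably small. The illustrated error, roughly two to three times nominal for a false result in favour of ultrasound, assumes 22 analysed per arm, equal true patency, and one crossover who would also have failed at six months. With no crossovers it is zero.

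A reader might infer two stronger things. One is that the trial is likely to produce a false win for ultrasound. That would need crossover rates of 10 to 20%, and the highest early-failure rate in Appendix 1 is 7%. The other is that the comparison is unbiased only if every crossover is kept as an ultrasound failure. The documents do not support that either, because the trigger is undefined and prescribes re-treatment in one arm only.

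**What to change.** 1. Section 3.9: make the primary analysis include all patients in the arm to which they were randomised. Define the per-protocol set and use it only as a sensitivity analysis.
2. Section 3: describe the two groups by randomised allocation instead of by the procedure received.
3. Sections 3.1 and 3.9: define loss of primary patency by the same objective criteria in both arms, drawn from the flow, venous pressure and symptom measures already collected. Set the same re-intervention trigger for both arms. Count any re-intervention that meets the trigger, including crossover to fluoroscopy, as loss of primary patency in the randomised arm. Report patency after re-treatment separately.

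The cost is wording in three sections and one case-report field for a repeat intervention and its date. No visit, procedure or patient is added. The downside is that ultrasound patency may look slightly less favourable than under per-protocol handling.

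### The rule for a negative first follow-up contradicts itself on refractory stenoses and sends patients one way, to fluoroscopy; with no patency rule for repeat procedures and a per-protocol analysis, it can bias the primary comparison.

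*Combined protocol and SAP*

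**What the plan says.** Section 3.1 of the combined protocol and SAP sets the rule off with "In the event of a negative outcome during the first post fistuloplasty follow-up, it will be determined whether it is due to" and gives two causes: "a missed stenotic segment invisible to ultrasound or" and "it is a case of severe stenotic segment refractory to fistuloplasty".

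- **Missed segment:** "Patients belonging to the former category will cross-over to the fluoroscopic-guided fistuloplasty group".
- **Refractory stenosis:** "In the latter case, there is no reason to repeat the fistuloplasty regardless of the imaging method (ultrasound or fluoroscopy". The text continues "Ideally, these particular patients should receive drug-coated balloon (DCB) fistuloplasty which is beyond the scope of this study" and closes with "There is no alternative apart from switching to fluoroscopic-guided fistuloplasty".

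Sections 3.1 and 3.8 put the first follow-up at two weeks. Section 3.1 makes the primary outcome a comparison of patency at one, three and six months. It does not define patency or say whether a second procedure ends it. Section 3.9 says "The data collected will be analyzed using an per protocol basis" and does not mention crossovers.

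**The concern.** Two investigators faced with the same refractory stenosis could act in opposite ways and each cite section 3.1. One would leave the access alone; the other would repeat the procedure under fluoroscopy. That choice may determine whether the access is open at the primary time points.

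The redirection also runs one way. A patient randomised to ultrasound can be sent to fluoroscopy, whereas a patient randomised to fluoroscopy has nowhere to cross to. Since neither the outcome definition nor the analysis section says how a redirected patient is scored, the same clinical course can be recorded as a failure, an exclusion, a fluoroscopy patient or a success. Unless the handling is fixed in advance and is the same in both arms, the primary comparison can be biased by following the plan as written.

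**Working it through.** **1. Setting the sentences side by side.**

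| Branch | Can occur in | Action directed |
|---|---|---|
| Missed segment not visible on ultrasound | Ultrasound arm only | Cross over to fluoroscopy |
| Refractory, first sentence | Either arm | No repeat under either imaging method |
| Refractory, last sentence | As an action, ultrasound arm only | Switch to fluoroscopy-guided fistuloplasty |

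A switch to fluoroscopy-guided fistuloplasty is itself a repeat fistuloplasty, so the last two rows conflict. For a fluoroscopy patient with an early negative outcome, the only text that could apply is the no-repeat sentence.

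**2. Timing.** The rule acts at two weeks. The primary time points are one, three and six months, so every one of them falls after the redirection.

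**3. The plan's own sample size (section 3.6).** Inputs: 90% and 52.4%, alpha 0.05, power 80%. Two-sided test, pooled variance, no continuity correction, mean rate 0.712:

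n = [1.96·√(2·0.712·0.288) + 0.842·√(0.90·0.10 + 0.524·0.476)]² / 0.376² = 21.6, so 22 per group, as stated. The stated 27 is 22 × 1.2 = 26.4, rounded up. The planned difference is 90 − 52.4 = 37.6 points.

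**4. How many patients could be affected.** The documents give no two-week failure rate. The nearest figures in time are the one-month ultrasound patencies in Appendix 1: 93, 94.4, 96 and 100%. As an assumed proxy, the early failure rate is 0–7%:

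- 27 × 0.07 = 1.9, so about 0–2 of 27 patients.
- If 2 failures are counted as patent: 2/27 = 7.4 points.

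**5. What the missing rule does to one set of results.** Assumed counts: 22 ultrasound patients, of whom 18 are patent at six months, 2 fail late and 2 fail early and are switched.

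| Handling of the 2 switched patients | Ultrasound patency |
|---|---|
| Counted as failures | 18/22 = 81.8% |
| Dropped | 18/20 = 90.0% |
| Rescued and counted as patent | 20/22 = 90.9% |

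**6. Direction.** Assume the fluoroscopy arm has the same true result, 18/22 = 81.8%, with its early failures counted as failures.

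- Dropped from ultrasound only: 90.0 − 81.8 = 8.2 points in favour of ultrasound.
- Rescued and counted as patent in ultrasound: 90.9 − 81.8 = 9.1 points.
- Moved to fluoroscopy and not patent there: 90.0 − 18/24 (75.0%) = 15.0 points.
- Moved to fluoroscopy and patent there: 90.0 − 20/24 (83.3%) = 6.7 points.

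With moved patients counted as patent, the size and sign depend on the underlying rate. At 52.4% in both arms the gap is 57.6 − 56.4, about 1.3 points before rounding. For x patients moved out of n per arm, the sign turns when true patency is below (n − x)/(2n) = 20/44 = 45.5%. Moving also works against ultrasound if the benchmark is as-randomised patency with rescues counted as patent: the gap falls from 9.1 to 6.7 points.

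**The case against.** The strongest case on the other side has four parts.

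- **The rule is not confined to one arm.** The trigger names no arm, and the no-repeat sentence covers both imaging methods. This stands. A reader might infer that the whole rule is written for the ultrasound arm only; the documents do not support that. What is specific to ultrasound is the missed-segment category and every procedure directed.
- **The last sentence has no stated subject.** It could return to the missed-segment group, which would remove the conflict. That reading is possible, but the sentence directly follows the one about the refractory patients. At best the text is ambiguous, and it needs the same repair.
- **The figure in section 3.1 and the flowchart are not shown.** Either might set out the crossover path. They cannot be relied on either way; no text available for review supplies the rule.
- **The direction and size of any bias are not given.** This stands. Nothing says that ultrasound failures are removed or rescued while fluoroscopy failures count in full. A refractory ultrasound patient who is not re-treated may simply remain a failure.

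A reader might also reach a larger figure from the 84% technical success in Appendix 2: 27 × 0.16 = 4.3, about 4 patients, and 4/27 = 14.8 points. That is not a sound basis. Technical success is judged on the table in this protocol, whereas the rule acts at two weeks; and the 84% comes from one series of 43 patients, while every other reported ultrasound figure in that appendix is 93% or higher.

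**Conclusion.** The concern holds in this form: the refractory branch is contradictory on its plain reading, the redirection is one-way and precedes every primary time point, and neither the outcome nor the analysis section says how a redirected patient counts.

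If early ultrasound failures are dropped, or rescued and counted as patent, the comparison favours ultrasound. If they are moved to the fluoroscopy group, the size and possibly the direction depend on their later course, the underlying patency and the benchmark. The documents do not establish that the trial will favour ultrasound, only that the plan leaves this open.

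The likely size is modest: about 0–2 of 27 patients and up to about 7 points, against a planned 37.6. This rests on one-month patency standing in for two-week failure, and the protocol does not define a negative outcome. The 81.8%, 90.0% and 90.9% results use assumed counts and show sensitivity to handling; they are not forecasts. With 22 to 27 patients per arm, one or two patients are enough to matter.

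**What to change.** **Protocol, section 3.1.** The sponsor must reconcile the sentences on refractory stenosis into one instruction and state what applies to an early negative outcome in each arm. Which management is right is a clinical decision outside this review.

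**Analysis, section 3.9.**

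1. Make the primary patency analysis as randomised, with per protocol as a sensitivity analysis.
2. Count any repeat fistuloplasty, crossover or switch, in either arm, as loss of patency from its date.
3. Score a patient with a negative outcome who is not re-treated by the same patency criteria in both arms, so that neither reading of the clinical rule leaves a patient unscored.

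**Cost.** A protocol clarification and a few sentences in section 3.9, with no added visits. The real price is that ultrasound patency, and so the observed difference and power, may be lower than planned. As an illustration, if two patients move from patent to failed in the ultrasound arm only, 90% becomes 90 − 7.4 = 82.6%. Against 52.4%, the section 3.6 formula (mean rate 0.675) solved for power at 22 per group gives z = [0.302·√22 − 1.96·√(2·0.675·0.325)] / √(0.826·0.174 + 0.524·0.476) = 0.19, a power of about 57% instead of 81%. If the planned 90% already treats repeat procedures as failures, which the documents do not say, this loss does not arise.
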